#### **9.4.4 Sensitivity analyses**

As a supportive analysis, summary statistics will be provided for the PPS.

### **9.5 Analysis of secondary variables**

#### **9.5.1 Efficacy variables**

##### **9.5.1.1 Spirometry**

All spirometric efficacy variables will be analyzed for the FAS, unless otherwise specified. Spirometry measurements taken within 7 days of systemic corticosteroid use and/or within 6 hours of rescue medication use will be set to missing and not be imputed, unless specified otherwise.

Summary statistics will be provided for pre-dose trough FEV1 and post-dose FEV1 (30 min, 1 hr) by visit and by treatment. Similar analyses will be performed for pre- and post-dose FVC and change from baseline in the spirometry values.

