### **5.6.2 Discontinuation of study treatment**

Discontinuation of study treatment for a patient occurs when study drug is stopped earlier than the protocol planned duration, and can be initiated by the patient, patient's parent/ legal guardian, or the investigator.

The investigator must discontinue study treatment for a given patient if, on balance, he/she believes that continuation would negatively impact the risk/benefit of trial participation.

Study treatment *must* be discontinued under the following circumstances:

- Patient's or parent/ legal guardian's wish
- Administration of a prohibited medication ([Table 5-1](#) and [Table 5-3](#))
- Worsening asthma as defined in [Section 6.5.6](#), as well as the following.
  - Excessive use of rescue medication (more than 200 µg salbutamol/ 180 µg albuterol four times per day for three consecutive days)
  - Abnormal test procedure results indicating risk for the patient on continued inhalation of the study drug including:
- Decline in PEF from the baseline PEF of  $\geq 20\%$  for one day or  $\geq 15\%$  for 3 consecutive days. The baseline PEF for the Run-in epoch would be the PEF taken at Visit 101. The baseline PEF (morning and evening) for the treatment epoch is calculated at visit 199 and is the mean of the best of the three daily PEF measurements over the past 14 days.
- Patients who experience moderate or severe asthma exacerbations ([Section 6.5.7](#))
- ECGs:
  - If the absolute QTcF  $\geq 450$  msec or an increase from baseline of  $> 60$  msec on 2 adequate ECGs at least a minute apart
  - 2nd or 3rd degree AV block
  - Atrial or ventricular arrhythmias (as judged clinically significant by the investigator)

- Any severe or serious adverse event considered possibly related to the study medication
- Patients who experience paradoxical bronchospasm: dyspnea and wheezing significantly increasing shortly after the administration of bronchodilator (*see Investigator's Brochure for more details*)
- Adverse events for which continued inhalation of the study drug would be detrimental
- If a patient develops a medical condition that requires use of prohibited treatment as per [Section 5.5.8](#), or if patient exhibits a behavior of non-compliance regarding prohibited medications.
- Pregnancy (see [Section 7.5](#))
- Any situation in which study participation might result in a safety risk to the patient

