#### **Asthma Worsening Criteria**

- Excessive use of rescue medication (more than 200 µg salbutamol/ 180 µg albuterol four times per day for three consecutive days)
- Decline in PEF from the baseline PEF of  $\geq 20\%$  for one day or  $\geq 15\%$  for 3 consecutive days.
- 20% decrease in FEV1 from baseline value (this criterion applies to Investigator review at the time of a study visit and an alert setting in the Masterscope)
- $< 60\%$  of PEF compared to baseline
- Night time awakenings requiring SABA use on at least 2 out of any 3 consecutive nights (patients may be continued in the study based on their general pattern of night time symptoms as per investigators judgement)

- Urgent unscheduled clinic visit due to asthma related deterioration

**Note:** The baseline FEV1 and PEF for the Run-in epoch would be the FEV1 and PEF taken at Visit 101. The baseline FEV1 for the treatment epoch is the mean of the 45 min and 15 min pre-dose FEV1 measurements at Day 1. The baseline PEF (morning and evening) for the treatment epoch is calculated at visit 199 and is the mean of the best of the three daily PEF measurements over the past 14 days.

If patients develop any of the above criteria, the patient should notify the investigator and be evaluated by the investigator and treated as clinically appropriate.

If any of the above criteria are met while a patient is in the Run-in epoch of the study, they may be withdrawn if, in the opinion the investigator, it is appropriate to do so.

Patients should also be withdrawn for safety reasons if, in the opinion of the investigators, it is appropriate to do so.

Worsening of asthma symptoms may require unscheduled evaluation between visits. Study site personnel must be available to monitor and document patient's progress until asthma control is regained.

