## 9.2 Patient demographics and other baseline characteristics

Demographic and baseline characteristics measured before randomization age, gender, race, ethnicity, height, weight, body mass index (BMI), relevant medical history, screening spirometric parameters (FEV1, FVC, FEV1/FVC), FEV1 reversibility, predicted and percentage of predicted FEV1, duration of asthma, history of asthma exacerbations, smoking exposure, prior concurrent medications (non-asthma and asthma-related), vital signs (systolic and diastolic blood pressure, pulse rate), peripheral blood eosinophil counts, QTc using Fridericia's correction and baseline ACQ-IA will be summarized by treatment group.

Continuous variables will be summarized using descriptive statistics (n, mean, 25th percentile, median, 75th percentile, standard deviation, minimum and maximum) and categorical variables will be summarized in terms of the number and percentage of patients in each category.

Baseline is defined as the last measurement before first dose of study drug.

No statistical analyses will be provided for baseline comparability among the treatment groups.

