### **9.5.2 Safety variables**

All safety parameters will be summarized on the safety set.

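### Post-dose FEV1 readings that follow rescue are dropped, and Visit 299 change is taken only from Day 1, so detection of acute post-dose falls is weakened

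*Protocol*

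**What the plan says.** Table 6-3 of the protocol schedules spirometry 30 minutes and 1 hour after the supervised dose at Visits 201 and 299. Section 9.5.1.1 plans: "Summary statistics will be provided for pre-dose trough FEV 1 and post-dose FEV 1 (30 min, 1 hr) by visit and by treatment". It adds FVC and "change from baseline in the spirometry values".

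The exclusion rule in the same section says: "Spirometry measurements taken within 7 days of systemic corticosteroid use and/or within 6 hours of rescue medication use will be set to missing". The sentence goes on to rule out imputation and leaves room for exceptions specified elsewhere.

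Section 9.2 gives the general reference: "Baseline is defined as the last measurement before first dose of study drug". The note in section 6.5.6 makes the treatment-epoch FEV1 baseline the mean of the two pre-dose values on Day 1. Section 6.5.6 also lists a 20% FEV1 decrease from baseline as a sign of worsening asthma, and adds that "this criterion applies to Investigator review at the time of a study visit" and to a spirometer alert.

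Section 5.6.2 lists among the mandatory reasons to stop treatment: "Patients who experience paradoxical bronchospasm: dyspnea and wheezing significantly increasing shortly after the administration of bronchodilator".

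Section 9.5.2 opens with "All safety parameters will be summarized on the safety set". It then covers adverse events, ECG, vital signs and laboratory data, but not spirometry. For ECG and vital signs it keeps all data whether or not rescue was used.

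**The concern.** An acute airway response to the inhaled powder would show in the first hour after a dose. Home PEF cannot show it, because section 6.4.4 times PEF just before the morning dose and 12 hours later. That leaves the two clinic readings, which the plan uses only as efficacy data.

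In that role, two stated rules work against seeing a fall.

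- The rescue deletion is informative. Rescue in the 6 hours before a visit normally leads to rescheduling (sections 3.1 and 5.5.6). Most post-dose readings still open to deletion therefore belong to children who needed salbutamol after the dose.
- At Visit 299 the change score sets a post-dose value against a pre-dose value from two weeks earlier, so bronchodilation gained in between can cover a same-day drop.

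The trial informs the choice of paediatric dose from descriptive summaries of two active arms with no placebo. Section 3.6 says that safety data at this age are limited. One or two acute responders in one arm would be relevant, and the post-dose summary is biased favourably in whichever arm has more of them.

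**Working it through.** **Inputs.** The plan gives no figure for this point. Its sample size reproduces: 72/(1 - 0.10) = 80 randomized (section 9.7), which at 1:1 is 80/2 = 40 per arm, or 72/2 = 36 evaluable per arm. Reading times of 30 and 60 minutes come from Table 6-3, and the 6-hour window from section 9.5.1.1. Rescue times, trough gains and FEV1 changes in mL are assumptions, because the protocol states none.

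**Step 1: which readings the rescue rule removes.** Section 5.5.6 applies the window to rescue taken before spirometry. On that reading a value is deleted if 0 ≤ (reading time - rescue time) ≤ 360 minutes.

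| Rescue, min after dose | Deleted | Kept |
|---|---|---|
| 10 or 20 | 30 and 60 min | none |
| 35 or 45 | 60 min | 30 min |
| 70 | none | 30 and 60 min |

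Section 9.5.1.1 does not itself state a direction. Read in either direction, every row would lose both values.

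**Step 2: the Day 1 reference.** Let g be the trough gain since Day 1 and f the same-day post-dose fall. The apparent change from Day 1 is (1 + g)(1 - f) - 1. The same-day fall needed to read as -20% is 1 - 0.8/(1 + g).

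| g | 20% fall reads as | 12% fall reads as | Fall needed to read -20% |
|---|---|---|---|
| 0 (Visit 201) | -20.0% | -12.0% | 20.0% |
| 5% | -16.0% | -7.6% | 23.8% |
| 10% | -12.0% | -3.2% | 27.3% |
| 15% | -8.0% | +1.2% | 30.4% |

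For example, 1.10 × 0.80 - 1 = -0.12, and 1 - 0.8/1.10 = 0.273. In litres, take an assumed Day 1 baseline of 1.50, Visit 299 pre-dose value of 1.70 and post-dose value of 1.36. The same-day ratio is 1.36/1.70 = 0.80, a 20% fall. Against Day 1 it is 1.36/1.50 = 0.907, a 9.3% fall.

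At Visit 201, g is zero by definition, so nothing is masked. The 20% alert in section 6.5.6 uses the same Day 1 baseline, so at Visit 299 it shares the offset.

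**Step 3: what deletion does to an arm mean.** Assume 35 children at +150 mL and one at -400 mL. With all 36 the mean is (35 × 150 - 400)/36 = 134.7 mL, and with the one deleted it is 150 mL, a shift of 15.3 mL. For -200 and -600 mL the shifts are 9.7 and 20.8 mL. One deleted child moves the mean little, and one retained child would barely show in it. The information lies in the individual values.

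**The case against.** The strongest reply is that the protocol identifies this harm clinically, by breathlessness and wheeze soon after dosing, and reports it as an adverse event. Section 9.5.2 summarizes and lists treatment-emergent events and tabulates those leading to discontinuation, with no rescue exclusion. Both clinic doses are supervised, with assessments from 15 minutes. The deletion rule stands under efficacy variables and allows exceptions, so it does not touch the raw values behind the section 6.5.6 alert. Most of this stands. A reader might infer that the plan cannot show acute falls at all, but the documents do not support that, since recognised events are captured.

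Three other stronger readings also fail. The Day 1 reference is no defect at Visit 201, where it is the same-day pre-dose value. A rescued child does not always contribute nothing, because readings taken before rescue are kept on the natural reading. Post-dose results need not look uniformly favourable, because unrescued children who fall stay in.

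Visit 299 is also the less likely setting. Children stopped earlier receive no study drug at a discontinuation visit (section 6), so those dosed at Visit 299 tolerated earlier doses. Trough and post-dose values at that visit are both summarized, so a fall across a whole group would be visible. Side-by-side group summaries do not, however, show one child's fall.

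Finally, the statistical analysis plan is not shown and may add such a listing. That limits the weight of the point but does not remove it: the deletion rule and the Day 1 reference are what the protocol states, and they are not merely details left open.

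**Conclusion.** The point holds in limited form. Objective detection of an acute post-dose fall is weakened in two situations: when a child is rescued before a reading, and when the fall occurs at Visit 299. In the first, one or both readings leave the only planned summary. In the second, a 20% same-day fall reads as about -16% to -8% for assumed trough gains of 5% to 15%, and a fall of 23.8% to 30.4% is needed to read as -20%. Falls at Visit 201 without rescue are shown in full.

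The size at Visit 299 rests entirely on the assumed gains, and the pattern of deletion rests on assumed rescue times and on reading the 6 hours as running forward from rescue. The protocol offers no estimate of how often either situation would arise. This is a worthwhile and cheap improvement to the safety reporting. It is not an error that invalidates the primary analysis.

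**What to change.** **Section 9.5.1.1.** Keep the rescue deletion, state that it applies to the efficacy summaries only, and state that the 6 hours run from rescue use to a later reading.

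**Section 9.5.2.** Add one table on the Safety Set, by dose and visit:

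- each child's lower FEV1 of the 30-minute and 1-hour readings, as percent change from that visit's own pre-dose mean, summarized with values after rescue kept and flagged;
- the number and percentage of children with a fall of 20% or more. This borrows the figure in section 6.5.6 as a descriptive reporting cut-off. It is neither a definition of paradoxical bronchospasm nor a stopping rule.

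Add a listing of rescued children with rescue time, number of puffs and the FEV1 values before and after.

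**Cost.** One table and one listing from spirometry already scheduled, with no change to visits, sample size or clinical management. Values after rescue understate the fall and do not recover the lowest point, so rescue use must be shown beside them.

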##### **9.5.1.2 ACQ-IA**

ACQ-IA score at each visit will be summarized by treatment groups. The proportion of patients who achieve an improvement of at least 0.5 in ACQ-IA (i.e. decrease of ACQ-IA score of at least 0.5 from baseline) at visit 299 will be summarized by treatment groups.

##### **9.5.1.3 Exposure to indacaterol in plasma following sparse pharmacokinetic (PK)**

Blood samples for PK analysis will be collected in all patients.

##### **9.5.1.4 Rescue medication**

The number of puffs of the rescue medication use in the last 12-hour is recorded twice daily (morning/evening) by the patient's parent/legal guardian in the e-Diary. The mean daily number of puffs (morning + evening) of rescue medication use over the 2 weeks of treatment will be summarized by treatment. The mean change from baseline in the daily number of

puffs of rescue medication use will be summarized by treatment. No imputation will be done for missing data. This analysis will be repeated for morning (nighttime) and evening (daytime) rescue medication use.

In addition, the percentage of 'rescue medication free days' (defined from diary data as any day where the patient did not use any puffs of rescue medication) will be summarized by treatment.

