#### **6.4.3 Electronic Diary**

At Visit 1, parents/ legal guardians will be provided with an e-Diary to record their child's rescue medication (salbutamol/albuterol) use. From Visit 101 on, they will record their child's clinical symptoms and PEF in the e-diary. The patient's parent/ legal guardian will be instructed to routinely complete the e-Diary twice daily – at the same time each morning and again approximately 12 hours later in the evening. The e-Diary is to be reviewed at each clinic visit until study completion. Sites and the patient's parent/ legal guardian will receive appropriate training and guidance on the use of the e-Diary device. A list of the Patient asthma control e-Diary questions is provided in [Appendix 4](#).

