#### **6.4.5 Rescue medication usage**

The use of rescue salbutamol/albuterol should be recorded by the patient's parent/ legal guardian in the e-Diary twice each day in the morning and evening. In the morning the

number of puffs of rescue medication their child has taken during the night and since the last diary entry, and in the evening the number of puffs of rescue medication the child has taken during the day since the morning diary entry should be recorded.

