## Appendix 4: Patient Asthma Control e-Diary

For illustrative purposes only

*The patient's parent/ legal guardian should assist the patient in completing the e-Diary.*

The following information will be captured:

---

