#### **Peak expiratory flow rate**

How often were you woken up by your asthma during the night?

Did you have asthma symptoms upon awakening in the morning?

Number of puffs of rescue medication during the past 12 hours

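### The morning rescue entry has an open-ended recall window in 6.4.5 but a 12-hour window in 9.5.1.4, so daytime puffs can be counted as night-time use after a missed evening entry

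*Protocol*

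**What the plan says.** Four places in the protocol define when and how rescue use is recorded.

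- **Section 6.4.5 (Rescue medication usage).** The morning entry is the "number of puffs of rescue medication their child has taken during the night and since the last diary entry". The evening entry is what "the child has taken during the day since the morning diary entry should be recorded".
- **Section 9.5.1.4 (Rescue medication).** "The number of puffs of the rescue medication use in the last 12-hour is recorded twice daily". Daily use is the sum of the morning and evening entries. The analysis is repeated with the morning entry as night-time use and the evening entry as daytime use. Missing data are not imputed.
- **Appendix 4 (e-Diary).** The morning and evening items both ask for "Number of puffs of rescue medication during the past 12 hours". The appendix is marked "For illustrative purposes only".
- **Section 6.4.3 (Electronic Diary).** Entries are to be made "at the same time each morning and again approximately 12 hours later in the evening".

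**The concern.** The analysis section assumes that a morning entry holds only night-time puffs. The collection section lets that entry reach back to whenever the diary was last completed. If the previous evening's entry was missed, the 6.4.5 window runs for about 24 hours and takes in the whole preceding day. Section 9.5.1.4 would still label the result night-time use. The no-imputation rule does not help, because the carried-over puffs sit inside an observed value.

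Rescue use is a named secondary objective (section 2.2). Section 9.4.2 bases dose selection on the totality of the data, without inferential testing, so descriptive summaries of this kind carry weight. The recall window is also an instruction for collecting data. An analysis plan can discard doubtful entries later, but it cannot tell from a recorded number which window the parent used.

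**Working it through.** The plan states no figure for rescue use or diary completion, so there is nothing to reproduce. The check compares the two windows and then sizes the effect under stated assumptions.

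**1. Windows side by side**

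| Situation | Morning value under 6.4.5 | Morning value under the 12-hour wording |
|---|---|---|
| Previous evening entry made, about 12 h earlier | night | night |
| Previous evening entry missed | previous day + night | night |

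Example: 0 puffs in the first night, 3 the following day, evening entry missed, 0 in the next night. The next morning's entry is 3 under 6.4.5 and 0 under the 12-hour wording. True night-time use is 0.

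**2. Formula**

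Let N be mean night use, D mean day use and p the chance that any entry is missed, independently. Under the open-ended window, unreported puffs pass to the next completed entry. The expected carry-over into a completed morning entry is

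D(p + p³ + …) + N(p² + p⁴ + …) = (pD + p²N)/(1 − p²).

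Divide by N for the relative overstatement. Multiply by 13/14, because the first of 14 mornings has nothing to carry over (a slight approximation).

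*70% of use by day (D/N = 7/3):*
- p = 0.05: 0.05 × (2.333 + 0.05)/0.9975 = 0.119; × 13/14 = 0.111
- p = 0.10: 0.10 × (2.333 + 0.10)/0.99 = 0.246; × 13/14 = 0.228
- p = 0.20: 0.20 × (2.333 + 0.20)/0.96 = 0.528; × 13/14 = 0.490

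*67% of use by day (D/N = 2):*
- p = 0.05: 0.05 × 2.05/0.9975 = 0.103; × 13/14 = 0.095
- p = 0.10: 0.10 × 2.10/0.99 = 0.212; × 13/14 = 0.197
- p = 0.20: 0.20 × 2.20/0.96 = 0.458; × 13/14 = 0.426

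**3. Simulation**

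Assumptions: 40,000 children, 14 days, Poisson use with N = 0.5 and D = 1.0 puffs, entries missed at random. The true daily mean is 1.5.

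| Entries missed | Night mean, 6.4.5 window | Overstatement | Night mean, 12-hour window | Daily mean on two-entry days, 6.4.5 window |
|---|---|---|---|---|
| 0% | 0.500 | 0% | 0.500 | 1.501 |
| 5% | 0.549 | 9.8% | 0.501 | 1.550 (+3.3%) |
| 10% | 0.598 | 19.6% | 0.500 | 1.598 (+6.5%) |
| 20% | 0.715 | 43.0% | 0.502 | 1.714 (+14.3%) |

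The simulation and the formula agree closely. With no missed entries both windows give the true values. With the 12-hour window and only two-entry days, the daily mean stays at 1.50 throughout.

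**The case against.** The strongest reply is that the windows coincide as the diary is designed. Section 6.4.3 spaces entries about 12 hours apart. On that schedule the last entry before the morning is the previous evening's, so 6.4.5 describes the same halves of the day that 9.5.1.4 analyses. The only diary question shown, in Appendix 4, agrees with 9.5.1.4. The protocol also requires one designated guardian to make all entries, trains families on the device and reviews the diary at each visit. All of this stands. It makes missed entries less likely, but it does not say what a parent should do after one, and there the two sections give different instructions.

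A reader might infer more than the documents support, in four ways:

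- **That every entry reaches back to the last one.** That phrase applies to the morning entry only. The evening entry runs from the morning entry, which is unclear if the morning entry was missed.
- **That values will be miscounted.** This follows only if a parent acts on the 6.4.5 wording. Under the 12-hour wording a missed entry leaves missing data.
- **That rescue-free days, and Day 14 in particular, are overcounted.** Such a day is "defined from diary data as any day where the patient did not use any puffs of rescue medication". In the simulation with the 12-hour window, counting one-entry days as full days raises rescue-free days from 22.3% to 24.7%, 27.2% and 31.1% at 5%, 10% and 20% missed. That treats a missing evening as zero puffs, which the protocol does not direct and a SAP can settle. It would arise even with matching wording.
- **That the dose comparison is biased.** Both blinded arms use the same diary and wording, so this needs adherence to differ by arm. Nothing in the protocol suggests that it will.

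**Conclusion.** The inconsistency is real and narrow. After a missed evening entry, the 6.4.5 instruction can put the previous day's puffs into a value that 9.5.1.4 analyses as night-time use. If no entry is missed and spacing is about 12 hours, there is no effect.

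The size cannot be known from the protocol. The range of roughly 10% to 50% for night-time use rests on four assumptions: 5% to 20% of entries missed at random, 67% to 70% of use by day, parents following 6.4.5, and full recall of the unreported puffs. It shows what is possible and does not forecast this trial. Change from run-in could be affected if adherence differs between run-in and treatment.

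The matter is minor, because the endpoint is secondary and only summarised. It is still worth correcting before data collection, since the window a parent used cannot be recovered afterwards.

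**What to change.** Use one recall window in 6.4.5, 9.5.1.4, Appendix 4 and the diary training text. The simplest choice is the past 12 hours, with the reference in 6.4.5 to the last diary entry deleted. If the open-ended window is kept instead, state that a half-day value is set to missing whenever the entry before it was missed.

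A sensible companion rule is to compute daily puffs and rescue-free days only on days with both entries, with those days as the denominator, in run-in and treatment alike. This can be left to the SAP.

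The cost is a wording change with no new data. The companion rule loses one-entry days from the daily summaries. Keeping the open-ended window also loses the half-day values that follow a missed entry.
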